## 9.1.4 Determining challenge outcome

For DBPCFCs challenge arms will be stopped and recorded as positive if one objective or two subjective symptoms occur (see table 1).

Table 1

Classification of the signs encountered during food challenges

1. Subjective

Oral itching, nausea, mild abdominal pain with no change in behaviour

2. Objective

Urticaria (>1 site), angioedema (>1 site), wheeze, reduced peak expiratory flow rate >/=20%, stridor, dysphonia, acute rhinoconjunctivitis, severe abdominal pain with behaviour change (e.g. doubling up, clinginess), vomiting, hypotension for age (not vaso-vagal), elevated serum mast cell tryptase (retrospective).

#### 9.2. Adverse events

Safety data will be recorded on a specifically designed case report form (CRF). All serious adverse events (SAEs) will be reported on an SAE report in addition to CRFs. Safety data will be reviewed periodically by the DMC. The DMC has the authority to withdraw any participant and/or terminate the trial because of safety findings.

Adverse events that are classified as serious must be reported promptly and appropriately to the NIHR, Cambridge University (sponsor), principal investigators in the trial, and the Ethics Committee. This section defines the types of adverse events and outlines the procedures for appropriately collecting, grading, recording, and reporting them. Information in this section complies with ICH Guideline E2A: Clinical Safety Data Management: Definitions and Standards for Expedited Reporting, ICH Guideline E-6: Guideline for Good Clinical Practice, and applies the standards set forth in the National Cancer Institute (NCI), Common Terminology Criteria for Adverse Events (CTCAE), Version 3.0 (December 12, 2003).

#### 9.2.1 Adverse Event definitions

An adverse event is any occurrence or worsening of an undesirable or unintended sign, symptom, laboratory finding, or disease that occurs during participation. An adverse event will be followed until it resolves or until 30 days after a participant terminates from the study, whichever comes first. A serious adverse event is defined as any adverse event that suggests a significant hazard. This includes but is not limited to any of the following:

1. Death: A death that occurs during the study must be reported whether considered treatment related or not.

2. A life-threatening event: A life-threatening event is any adverse therapy experience that, in the view of the investigator, places the participant at immediate risk of death from the reaction as it occurred.

3. Inpatient hospitalization or prolongation of existing hospitalization.

4. Persistent or significant disability.

5. An event that requires intervention to prevent permanent impairment or damage. An important medical event that may not result in death, be life threatening, or require hospitalization may be

considered an SAE when, based on appropriate medical judgment, it may jeopardize the participant and may require medical or surgical intervention to prevent one of the outcomes listed above. 6. Other conditions specified in the protocol.

An adverse event is considered as 'unexpected' when its nature or severity is not consistent with the investigator's protocol.

#### 9.2.2 Collection and recording of adverse events

Adverse events will be collected from the time the participant provides consent until the time the event resolves or until 30 days after the participant completes study treatment. Adverse events may be discovered through observing and questioning the participant or receiving an unsolicited complaint and questioning the participant in an objective manner. Throughout the study, the investigator will record all adverse events on the appropriate adverse event CRF regardless of their severity or relation to study medication or study procedure. The investigator will treat participants experiencing adverse events appropriately and observe them at suitable intervals until their symptoms resolve or their status stabilizes. SAEs will be recorded on the adverse event CRF and health authorities notified.

#### 9.3 Grading and attribution of adverse events

#### 9.3.1 Grading Criteria

The study site will grade the severity of adverse events experienced by study participants according to the criteria set forth in the NCI-CTCAE Version 3.0. This document provides a common language to describe levels of severity, to analyze and interpret data, and to articulate the clinical significance of all adverse events. Adverse events will be graded on a scale from 1 to 5 according to the following standards in the NCI-CTCAE manual: Grade 1 = mild adverse event. Grade 2 = moderate adverse event. Grade 3 = severe and undesirable adverse event. Grade 4 = life-threatening or disabling adverse event. Grade 5 = death. All adverse events will be reported and graded whether they are or are not related to disease progression or treatment.

#### 9.3.2 Attribution Definitions

The relation, or attribution, of an adverse event to study participation will be determined by the investigator and recorded on CRF and/or SAE reporting form. The relation of an adverse event to the study treatment will be determined using the descriptors and definitions provided in Table 1. For additional information consult the NCI-CTCAE web site: http://ctep.cancer.gov/reporting/ctc.html.

#### 9.4 Reporting serious adverse events

#### 9.4.1 Timeline

Serious adverse events must be reported to the PI within 24 hours

**9.4.2 Options for Reporting Serious Adverse Events** All SAEs will be reported to the Cambridge LREC, DMC AND NIHR where in the opinion of the Chief Investigator the event was related (resulted from the administration of any of the research procedures) and unexpected (an event not listed in the protocol as an expected occurrence). Reports will be submitted within 15 days of the CI being made aware of the event.

**10. Proposed sample size:** The study will be carried out at a single centre (Wellcome Trust Clinical Research Facility at Addenbrookes Hospital, Cambridge). We will enroll 104 subjects, with an estimated 49 randomized to each group (including a 5% uplift to account for withdrawals). Package 1 Aim: A randomized controlled comparison of intervention versus waiting list control For the primary analysis a Fisher's exact test will have 90% power, using a 0.05 two-sided significance level, to detect a difference between group percentages passing the peanut challenge test of 64% vs 30% when the sample size per group is 49 (reference: nQuery 4.0, StatSol Ltd, Ireland). Allowing for just over 5% loss-to-follow-up rate this implies recruiting 104 participants overall to be allocated equally into the active intervention vs waiting list control groups.

Package 2 Aim: To confirm efficacy in the waiting list group when treated, alone and in combination with the active group to allow overall estimate of success rate to within 10%. It will be possible to conclude the true efficacy of the intervention would be within 10% of the overall sample-based point estimate when combining those who received the intervention with or without a waiting period, anticipated to be approximately n=35 and n=50, respectively, with 95% confidence

## 11. Statistical analysis:

## 11.1 Analysis samples

The following groups will form samples for analysis

11.1.1 Intention to treat: All subjects allocated to each arm will be analyzed together as representing that treatment arm, whether or not they have completed the prescribed regimen.
11.1.2 Per protocol analysis: The criteria for per protocol analysis of the outcome of peanut challenge at the end of immunotherapy will consist of: Tolerance and continuation of immunotherapy up to 800mg protein

#### 11.2 Endpoint analysis

**11.2.1 Analysis of primary endpoint**: The main analysis will compare the proportion of subjects who pass a peanut challenge in the intervention and control arms six-seven months after randomization, using a Fisher's exact test at the p<0.05 level of significance.

**11.2.2 Analysis of secondary endpoints**. Quality of life scores will be compared before and after intervention by pair wise comparison within individuals, and group medians will be compared using methods for non-parametric data. The results of cellular and humoral assessments of immune responses will be compared using methods for non-parametric data (e.g. comparison of medians of serum peanut specific IgG4 at different time points by Mann-Whitney U test). The incidence of adverse events will be compared between the intervention and control groups using a two-tailed Fisher's exact test at the p<0.05 level of significance. For package 2, the proportion of patients who may expect success will be calculated, with 95% confidence intervals. The influence of severity, age, sex, other allergy on immunotherapy success will be assessed by multiple logistic regression analysis.

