#### 3.3.4 Group allocation

Within an individual various factors including severity of allergy (from history and challenge), age, presence of asthma, and other active allergies, are known to influence reactivity and thus may influence the successful response to immunotherapy. Random group allocation may result in an imbalance of these factors between the active and control groups, leading to bias. To account for this, subjects will be allocated using minimization, with a random element using a weighting probability of 0.8.

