#### 5. Research design

**5.1 Design.** This is a randomized controlled trial of a novel active intervention (peanut oral immunotherapy) versus the status quo (peanut avoidance) in 104 participants (7-18yrs) with peanut allergy (figure 1). One hundred and four participants will be recruited and undergo characterization by history, allergy testing, blinded peanut challenge and quality of life questionnaire. Peanut allergy will be confirmed in all participants by DBPCFC. Subjects are then allocated to either active or control group. Central minimization with weighting will be used to account for variation in severity of reaction (from history and challenge), peanut threshold dose (from challenge), age, sex, asthma, and allergies to other foods. After six-seven months subjects will undergo a DBPCFC (primary outcome measure). Subjects in the control group will receive current best management (a comprehensive management plan focusing on peanut avoidance) for six-seven months followed by DBPCFC. Those in the control group who still have a diagnosis of peanut allergy will be invited to undertake peanut oral immunotherapy followed by a final peanut challenge.

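### The primary test ignores the six factors used to minimise allocation; an adjusted comparison that holds its level would match the design and gain some power, though the unadjusted test is valid

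*Protocol*

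**What the plan says.** Section 5.1 describes the allocation: "Central minimization with weighting will be used to account for variation in severity of reaction", and goes on to list threshold dose, age, sex, asthma and allergies to other foods. Section 3.3.4 adds that "subjects will be allocated using minimization, with a random element using a weighting probability of 0.8". Its reason is that factors such as severity, age, asthma and other allergies "are known to influence reactivity and thus may influence the successful response to immunotherapy", so that chance imbalance could bias the comparison.

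Section 11.2.1 then compares pass proportions between arms six to seven months after randomisation, "using a Fisher's exact test at the p<0.05 level of significance", with no covariates. Section 10 sizes the trial for that same test: "a Fisher's exact test will have 90% power, using a 0.05 two-sided significance level", for "64% vs 30% when the sample size per group is 49". The only covariate model is the logistic regression in Section 11.2.2. It asks which baseline features predict success of immunotherapy and is not a treatment comparison.

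**The concern.** Minimisation makes the arms more alike on the chosen factors than chance would. An unadjusted test still judges the difference against a reference distribution that allows for chance imbalance in those factors. If they predict outcome, that distribution is too wide and the test is conservative. Fisher's exact test is already conservative because it is discrete, so the two effects add.

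What is at stake is power. The factors are all recorded before allocation and the protocol thinks them important enough to balance, but the main test makes no use of them.

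**Working it through.** **Inputs from the protocol.** Two-sided 0.05; 64% v 30%; 49 per group; 104 recruited 1:1 (Section 10). Minimisation with probability 0.8 (Section 3.3.4) on six factors (Section 5.1).

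**Input that must be assumed.** The strength of the factors. The range below starts at no effect.

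**1. The plan's own figure.** Power is the sum, over all pairs (a, b) with Fisher p ≤ 0.05, of Bin(a; 49, 0.64) × Bin(b; 49, 0.30). This gives 90.6%. With 48 per group it is 89.6%, so 49 is the smallest number that reaches 90%. For recruitment, 98 / 0.95 = 103.2, rounded up to 104. The sample size statement reproduces.

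**2. Actual size of Fisher's test, no minimisation.** The same sum with equal rates in both arms:

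| Common pass rate | Exact size |
|---|---|
| 5% | 0.7% |
| 10% | 1.7% |
| 20% | 2.8% |
| 30% | 3.0% |
| 50% | 3.3% (the maximum) |

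Discreteness alone therefore keeps the level at or below 3.34%.

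**3. What minimisation adds.** Simulation of 98 participants with six independent binary factors, minimisation at 0.8, and 6,000 runs per scenario. The Monte Carlo standard error is about √(0.05 × 0.95 / 6000) = 0.3 points for a size of 5%. The adjusted test is the treatment coefficient in a linear model for pass/fail with all six factors. Size is at a common pass rate of 30%; power is at 64% v 30%.

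| Odds ratio per factor (joint AUC) | Fisher size | Adjusted size | Fisher power | Adjusted power | Gain, points |
|---|---|---|---|---|---|
| 1 (0.50) | 3.2% | 5.1% | 91.0% | 92.7% | about 2 |
| 1.65 (0.66) | 2.8% | 4.8% | 91.5% | 94.6% | about 3 |
| 2.7 (0.77) | 2.1% | 5.2% | 93.3% | 97.0% | about 4 |
| 4.5 (0.84) | 1.3% | 4.8% | 94.2% | 99.0% | about 5 |

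Without minimisation, Fisher's size stays at 2.9-3.1% whatever the factor strength. The fall down the second column is therefore due to minimisation, and it is visible only when the factors matter. In the first row the factors carry no information, so the gain there comes only from using the full 5% level.

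**4. A smaller true effect.** At 55% v 30%, with four binary factors and 3,000 runs per scenario, power for Fisher's test and the adjusted linear test was:

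- odds ratios all 1: 67% and 73%
- all 1.5: 65% and 71%
- all 2: 68% and 77%
- 4, 4, 3, 2: 68% and 81%

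These gains are 6-13 points. Other runs with odds ratios up to 4, including a version with robust standard errors, widen the range to about 4-14.

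**5. A lower control rate.** Section 3.3.2 expects natural resolution well under 20% and uses 30% as a cautious planning value. Fisher's exact power is then 99.3% for 64% v 20%, above 99.9% for 64% v 10%, about 93% for 55% v 20% and 92% for 40% v 10%. Little is left to gain.

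**6. Which adjusted test.** In the same six-factor simulation the adjusted logistic score test had a size of 5.6-6.3% at a 30% pass rate and 6.3-7.1% at 10%. The linear model with ordinary standard errors stayed at 4.5-5.2% over both rates. A version with robust standard errors gave 4.4-5.0%, even at a 10% pass rate with six covariates.

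**The case against.** The case for leaving the plan alone is substantial. Fisher's test guarantees its level, is simple, and copes with few or no control passes. The trial was sized for it, and the promised power is met in every scenario examined (91-94% under minimisation at 64% v 30%). The protocol calls both planning rates conservative, and at the control rates it expects Fisher's power is already high. An adjusted logistic test would replace a conservative level with one above 5%. Supplementary adjusted analyses may also sit in a statistical analysis plan that is not at hand.

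Most of this stands, and it limits the weight of the point. Two parts do not. The excess size belongs to the logistic tests, not to adjustment as such, since the linear risk-difference model held its level. Nor is the choice of primary test left to a later document: Sections 10 and 11.2.1 both fix the unadjusted test.

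A reader might also infer that the factors are strongly prognostic and that minimising on them is what pushes the test well below 5%. The documents do not support this. Section 3.3.4 says only that the factors may affect response and gives no strength, and discreteness accounts for most of the shortfall.

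**Conclusion.** The mismatch between allocation and primary analysis is real, and adjustment is worth making. It is an improvement in efficiency and consistency, not the repair of an invalid test. Fisher's size is 3.0% at a 30% pass rate and 1.7% at 10% before minimisation has any effect. It falls to about 2-2.5% only with clearly prognostic factors, and to 1.3% only in the most extreme case assumed.

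The gain is about 2-5 points at 64% v 30% and about 4-14 points at 55% v 30%. It is small if the control rate is as low as expected and the active rate is near plan. These gains rest on assumed independent binary factors with odds ratios from 1 to about 4 each. The lower end mostly reflects recovering the unused part of the 5% level, and a cautious small-sample variance correction would shrink it.

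It would be wrong to conclude that the sample size is inadequate or that the type I error is threatened. The 90% power reproduces at 90.6%, and the error is on the conservative side.

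**What to change.** In Section 11.2.1, make the primary analysis a comparison of the arms adjusted for the six minimisation factors, by one of two methods named in advance:

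- a linear risk-difference model with robust standard errors, with the small-sample correction stated; or
- a score test for treatment with its p-value obtained by re-running the minimisation.

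Both stay defined when few or no controls pass. An ordinary adjusted logistic test read against its usual reference distribution should not be used, because its size exceeds 5% here. State how each factor enters the model, report the adjusted risk difference with a 95% CI, and keep Fisher's exact test as a supportive analysis.

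The cost is one paragraph and slightly more programming, and the primary test becomes less simple to explain. No new data are needed because every factor is recorded before allocation. The sample size need not change.

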Our strategy for identifying these biomarkers and indicators will involve longitudinal comparisons of immune-response profiles over time within individuals, as tolerance is achieved (or when it is unsuccessful). We will also compare immune-response profiles between individuals on the control arm and those on the active intervention arms. Qualitative, quantitative, and time-dependent changes in allergen immune-response profiles of participants who do or do not develop tolerance to peanut will provide data for testing current hypotheses and generating new hypotheses to explain underlying tolerogenesis mechanisms. To identify the biomarkers associated with underlying tolerance mechanisms in operation at the time of sampling, we will perform analysis of the immune-response profiles at enrolment and at 14 days (early-point), 75 days (mid-point) and 150 days (latepoint) after active intervention or avoidance. Integration of biological responses with clinical outcomes will provide a means to identify the potential biomarkers outlined above. Assays at these time points for all subjects will include:

•Total and crude peanut-specific IgE, peanut-specific IgG and IgG4

•Ara h 1-3, 8 and 9-specific IgE, IgG and IgG4 will be measured

Peanut specific T helper cell proliferation and cytokine response (supernatant IL-4/IFN gamma and IL-10 by ELISA; intracellular IL-4, IFN gamma and IL-10 by flow cytometry)

In a subset of older subjects able to provide a larger blood volume (200mls; >14yrs) we plan :

- Isolation of basophils and assay of activation markers CD63 and CD203c measured by flow cytometry during peanut allergen stimulation.
- Ratio of histamine HR1 to HR2 receptor mRNA on basophils by semi-quantitative polymerase chain reaction

Specimens may also be used in future immune response or biomarker assays to re-evaluate biological response as research tests are developed.

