## 8.2 Secondary Endpoints

- -
- The proportion of participants from the control group who pass a peanut challenge after receiving the active intervention
- The fold increase and absolute increase in threshold (amount of peanut protein tolerated) for the active and control group members after intervention.
- Quality of life scores in active treatment group after intervention and in control group after waiting list control
- Quality of life scores before and after intervention for both active and control groups (disease-specific validated tool
- Immunological outcomes: results of cellular and humoral assessments of immune response related to the development of allergy or tolerance to peanut
- Safety outcomes; incidence and nature of adverse events
- Recruitment source: assessment of compliance and efficacy in groups recruited nationally and locally
- Compliance: assessments of acceptability and compliance during intervention

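### The only test named for the immune markers, Mann-Whitney U across time points, ignores that the time points come from the same children

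*Protocol*

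**What the plan says.** Section 11.2.2 assigns the cellular and humoral results to non-parametric methods in general. It gives one example, for one marker: "comparison of medians of serum peanut specific IgG4 at different time points by Mann-Whitney U test". No other test for immune data is named in the protocol.

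Section 3.3.9 describes two kinds of immune comparison. The first is "longitudinal comparisons of immune-response profiles over time within individuals". The second is between arms: "We will also compare immune-response profiles between individuals on the control arm and those on the active intervention arms". Profiles are taken "at enrolment and at 14 days (early-point), 75 days (mid-point) and 150 days (latepoint) after active intervention or avoidance", so each child contributes up to four values per marker.

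For quality of life, section 11.2.2 says: "Quality of life scores will be compared before and after intervention by pair wise comparison within individuals". It adds that "group medians will be compared using methods for non-parametric data". Section 8.2 lists as an endpoint "Quality of life scores in active treatment group after intervention and in control group after waiting list control", and separately lists before-and-after scores in both arms.

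**The concern.** Two values of IgG4 from the same child, taken weeks apart, are usually correlated. The Mann-Whitney test treats the two sets of values as coming from different people. It therefore carries the full between-child spread into its error term, although that spread cancels when each child is compared with their own earlier value.

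The example in section 11.2.2 thus does not fit the first comparison that section 3.3.9 sets out. What is at stake is the mechanism aim: describing early, middle and late changes and finding candidate biomarkers. That aim rests on repeated blood samples from children, and the named test would discard much of the information that repeated sampling provides.

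**Working it through.** **Inputs from the protocol.** The sample size is 49 per group (section 10). The only power statement there is for the primary endpoint: 90% for Fisher's exact test, 64% against 30%, two-sided 0.05. Exact enumeration gives 90.6% at 49 per group, and 98/0.95 rounds up to 104, so the planned numbers reproduce. No power, SD, correlation or effect size is given for the immune or quality-of-life endpoints.

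**Assumptions.** Values are normal on the analysis scale with equal SD (set to 1) at both time points. Within-child correlation ρ is 0.3, 0.5 or 0.7. The mean change d is 0.4 SD, with 0.3 and 0.5 SD as checks. n = 49.

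**Step 1: type I error, by approximation.** The difference between the two time-point means has true variance 2(1 − ρ)/n, but an independent-samples test assumes 2/n. Under no change its statistic therefore has SD √(1 − ρ) instead of 1, and the actual error rate is about 2[1 − Φ(1.96/√(1 − ρ))]:

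- ρ = 0.3: 1.96/0.837 = 2.34, giving 1.9%
- ρ = 0.5: 1.96/0.707 = 2.77, giving 0.6%
- ρ = 0.7: 1.96/0.548 = 3.58, giving 0.03%

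**Step 2: power, by approximation.** Let m = d√(n/2) = 0.4 × √24.5 = 1.98. Power of the independent-samples test is about Φ((m − 1.96)/√(1 − ρ)). Since 1.98 almost equals 1.96, this is about 51% at every ρ. Power of the paired test is about Φ(m/√(1 − ρ) − 1.96):

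- ρ = 0.3: Φ(2.37 − 1.96) = 66%
- ρ = 0.5: Φ(2.80 − 1.96) = 80%
- ρ = 0.7: Φ(3.61 − 1.96) = 95%

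**Step 3: simulation with the rank tests themselves.** Rank tests on normal data do slightly worse than these figures. Several independent runs agree to within about two percentage points on power; for the Mann-Whitney error rate they give 2.0–2.4%, 0.6–0.7% and 0.04–0.1%.

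| ρ | Mann-Whitney true type I error | Mann-Whitney power, d = 0.4 | Signed-rank power, d = 0.4 |
|---|---|---|---|
| 0.3 | 2.0–2.4% | 48% | 62% |
| 0.5 | 0.6–0.7% | 47–48% | 76–78% |
| 0.7 | 0.1% or less | 47–48% | 93–94% |

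The signed-rank test stays near 5% type I error throughout.

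**Step 4: other effect sizes.** Power, Mann-Whitney against signed-rank, at ρ = 0.3, 0.5 and 0.7:

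- d = 0.3: 27% v 40%, 24% v 51%, 19% v 75%
- d = 0.5: 69% v 81%, 73% v 92%, 77% v 99%

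The direction is the same in every setting. The size of the loss depends heavily on ρ.

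**Step 5: quality of life between arms.** With 49 per arm and an assumed 0.5 SD effect, a rank test on post-period scores alone has 66–67% power. ANCOVA on the baseline score has about 73%, 80% and 93% at ρ = 0.3, 0.5 and 0.7. This step assumes that post-period scores alone are compared, which section 11.2.2 does not say.

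**The case against.** Mann-Whitney is offered only as an example, for one marker. The operative commitment is to non-parametric methods in general, which already covers the signed-rank test. The example can also be read as active against control at each of several time points. Section 3.3.9 plans that comparison, and Mann-Whitney is valid for it. The authors specify pairing for quality of life in the same section, so they know the distinction.

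This lowers the certainty but does not remove the point. The phrase contrasts time points and mentions no arms. It is the only immune test named, so an analyst would tend to follow it. Even on the favourable reading, the within-child comparison is left with no named method.

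A reader might infer three stronger conclusions, which the protocol does not support:

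- **That the immune results would contain false positives.** With positive within-child correlation the error runs the other way: the test rejects too rarely.
- **That every immune measurement is committed to this test.** The text fixes a family of methods and gives one example.
- **That quality of life is analysed wrongly.** Section 11.2.2 already specifies a paired within-child comparison, which uses each child's baseline, and adds a comparison of group medians, which is valid between randomised arms. The before-and-after change is therefore not the only evidence. Baseline adjustment is neither named nor excluded, and a statistical analysis plan may settle it.

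**Conclusion.** The point holds for the immune markers. As worded, the example in section 11.2.2 applies an independent-samples test to what section 3.3.9 describes as comparisons within the same children, and the two sections should be made to agree.

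At an assumed 0.4 SD change in 49 children, the loss in power is about 14 percentage points at a correlation of 0.3 (48% to 62%), 28 at 0.5 (48% to 76%) and 46 at 0.7 (48% to 94%). These figures rest on assumed correlations and effect sizes and on normal data, so they show direction and plausible range, not the loss in this trial. Real within-child changes could be missed; whether they would be cannot be known from the protocol.

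Only secondary mechanistic endpoints are involved. The primary Fisher's exact comparison and the sample size are untouched. For quality of life there is no error to correct, only a possible gain in precision.

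**What to change.** In section 11.2.2, separate the two immune comparisons:

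- **Change over time within a child:** a paired method, either the Wilcoxon signed-rank test on each child's change from enrolment, or a repeated-measures mixed model on log values.
- **Active against control at a given time point:** the Mann-Whitney U test, as now.

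Optionally, state that the between-arm quality-of-life comparison adjusts for the baseline score (ANCOVA, on ranks if the scores are skewed). This is a choice for efficiency.

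The cost is a sentence or two of analysis wording. The samples and questionnaires are already scheduled, so no further visit, blood draw or participant is needed.

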#### 3.3.7 Future development

The current proposal will advise on efficacy, mechanism and safety, also showing persistence of effect in the short to medium term. We are committed to future study that will investigate the optimal duration of maintenance treatment for long-term tolerance. In other forms of immunotherapy a maintenance treatment period of several years is required to induce a 'permanent' cure. This study is likely to catalyze and boost healthcare development for related allergic diseases. Not only will it provide a clinical treatment for peanut allergy, addressing a potentially life-threatening allergy in up to 2% of the childhood population, but it will also stimulate development of immunotherapy for other potentially severe food allergies e.g. tree nuts, sesame, fish, lupin and severe egg and milk allergy. We are currently experiencing an expansion in new food allergies: kiwi, mustard, lupin, fruits etc. The current study will provide a model for studying desensitization for novel food allergies as they emerge. Further no expensive vaccine is required. We have designed this intervention using cheap materials so that the treatment can be replicated at minimal cost and made widely available.

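### For adverse events Section 11.2.2 states only a between-arm Fisher test at p<0.05, which says almost nothing about uncommon serious reactions and gives the treated controls no defined place

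*Protocol*

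**What the plan says.** Safety is one of the things the trial is meant to report on. Section 3.3.7 says "The current proposal will advise on efficacy, mechanism and safety", and Section 8.2 lists among the secondary endpoints "Safety outcomes; incidence and nature of adverse events". The only analysis stated for this endpoint is in Section 11.2.2: "The incidence of adverse events will be compared between the intervention and control groups using a two-tailed Fisher's exact test at the p<0.05 level of" […].

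The next sentence of Section 11.2.2 treats benefit differently: "For package 2, the proportion of patients who may expect success will be calculated, with 95% confidence intervals". Section 10 explains that this estimate combines children treated after and without a waiting period, "anticipated to be approximately n=35 and n=50, respectively, with 95% confidence". No corresponding estimate of an adverse event rate is stated, either per arm or for all treated children.

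The sample size in Section 10 comes from the primary endpoint: "Fisher's exact test will have 90% power, using a 0.05 two-sided significance level", for "64% vs 30% when the sample size per group is 49".

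**The concern.** A trial sized for a 34-point difference in pass rates has little power for a difference of a few points in serious reactions. A significance test is then a poor summary of the data: several serious reactions in treated children and none in controls would still be reported as not significant. A reader of the final report could take that as reassurance.

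There is also a gap in who and what the comparison covers. The primary analysis is tied to six-seven months after randomisation, but the adverse event comparison has no stated period. Controls who still have peanut allergy are offered immunotherapy after their second challenge. Their reactions on treatment are collected, because Section 9.2.2 runs collection until 30 days after study treatment, but Section 11.2.2 does not say where those reactions are counted. Section 11.1.1 analyses all children in the arm to which they were allocated. Taken literally with no period limit, it could place reactions to immunotherapy in the control arm.

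**Working it through.** **Inputs from the protocol.** 49 per group, two-sided 0.05, 64% v 30% and 104 recruited (Section 10); about 35 treated controls and 50 active children, 85 in all (Section 10); about 70% of pilot children with reactions (Sections 3.3.5 and 7.2). The protocol gives no rate of serious reactions for either arm, so those rates below are assumptions and are shown as a range.

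**Method.** Exact power is the sum of Bin(x; 49, p1) × Bin(y; 49, p2) over all tables (x, y) with a two-sided Fisher p of at most 0.05.

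**Reproducing the plan's own figure.** For 64% v 30% this gives 90.6%, in line with the stated 90%. The recruitment figure also follows: 2 × 49 = 98, and 98/0.95 = 103.2, rounded up to 104.

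**Smallest significant result with no control events.** With equal arms, p = 2 × C(49, x)/C(98, x).

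| Events, treated v control | p |
|---|---|
| 4 v 0 | 0.117 |
| 5 v 0 | 0.056 |
| 6 v 0 | 0.027 |

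Six events against none are needed.

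**Power for uncommon events, 49 per arm (assumed rates).** With a control rate of 0%, power is P(X ≥ 6) for X ~ Bin(49, p1).

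| Treated v control | Power | Missed |
|---|---|---|
| 5% v 0% | 3.5% | 96.5% |
| 6% v 1% | 4.6% | 95.4% |
| 7% v 2% | 5.4% | 94.6% |
| 10% v 5% | 6.1% | 93.9% |
| 15% v 10% | 5.9% | 94.1% |
| 10% v 0% | 36.5% | 63.5% |
| 15% v 0% | 76.4% | 23.6% |
| 20% v 0% | 94.5% | 5.5% |

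Using all 52 randomised per arm changes little: 5% v 0% has power 4.5%.

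**Power for common events.** With 70% in the treated arm and assumed control rates of 20%, 30%, 40% and 50%, power is 99.9%, 98%, 82% and 45%.

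**What an interval would show.** With zero events, the exact two-sided 95% upper limit is 1 − 0.025^(1/n).

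- n = 49: 1 − 0.025^(1/49) = 7.3%.
- n = 85: 1 − 0.025^(1/85) = 4.2%.
- 3 events in 85: exact 95% limits 0.7% to 10.0%.

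**Share of treated children with no defined place.** 35/85 = 41%.

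**Why the at-risk period matters.** Assume a 20% event rate on treatment and 0% off it. In the randomised period alone, power is 94.5%. If 35 of 49 controls are later treated and their events are counted in the control arm, power falls to about 7%. The protocol does not say that this will be done, but it does not exclude it either.

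**The case against.** The strongest reply is that the protocol nowhere makes this test its verdict on safety. A reader might infer that treatment safety is judged by the Fisher test, but the documents do not support that. It is one secondary comparison, and no section treats p>0.05 as a criterion. Section 5.2 has the Data Monitoring Committee reviewing safety throughout, and Section 5.3 stops enrolment pending review on a single event of the listed kinds, without any test. At a true 5% rate, the chance of at least one event among 49 treated children is 1 − 0.95^49 = 92%. Adverse events are also graded and attributed under Section 9.3.

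Second, the test concerns adverse events in general, not severe reactions. For the common reactions seen in the pilot its power is good over much of the plausible range of control rates. The rates for severe reactions are assumed, and the pilot reported no serious adverse events.

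Third, a reader might infer that the treated controls are excluded from the safety assessment. They are not: their events are collected, and the Section 8.2 endpoint has no limit by arm or period. Keeping a randomised comparison to the randomised arms is not an error.

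Fourth, exact limits and tables by grade often belong in a statistical analysis plan, which is not at hand, so their absence from the protocol is not in itself a fault.

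These points narrow the concern but do not remove it. Monitoring rules protect participants during the trial; they do not estimate risk for the final report. Good power for oral itching does not carry over to serious reactions. And the point rests on the method that the protocol does state, with no period attached, next to a sentence that plans intervals for benefit.

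**Conclusion.** The concern holds in a limited form. The stated adverse event analysis is adequate for common mild reactions and nearly uninformative for uncommon serious or grade 3 or higher ones. At 49 per arm it needs 6 v 0; it misses a 5-point excess about 94-97% of the time for control rates of 0-10%, and 10% v 0% about 63% of the time. These figures depend on assumed event rates. The 97% end needs exactly 5% v 0%, and for a 15-20% excess over zero the test does reasonably well. The 6 v 0 threshold and the upper limits need no assumed rate.

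The treatment of crossed-over controls is unspecified rather than wrong: the comparison has no at-risk period and no defined place for about 35 of 85 treated children. This is a cheap improvement to the reporting of harm. It does not invalidate the design, and it does not show that safety goes unmonitored.

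**What to change.** In Section 11.2.2:

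1. Limit the between-arm comparison of adverse events to the randomised period before controls cross over, and report the risk difference with a 95% confidence interval.
2. Add the proportion of children with serious and with grade 3 or higher events, with exact 95% limits, for each arm and for all children who received immunotherapy (about 85).
3. Keep the Fisher test as descriptive, and state that p>0.05 is not evidence of safety.

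All of this uses data already collected. The cost is a few lines of protocol or analysis plan text and a few extra table rows. The drawback is a less favourable safety statement, since an upper limit of about 4% would have to be quoted even with no events among 85 treated children.
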